**AbbVie Safety Korea**

**11.1.6 Pregnancy Reporting**

Pregnancies in patients will be collected from the date of the first dose through 150 days following the last dose of adalimumab taken during the study. In the event of a pregnancy occurrence in the patient, the physician will notify AbbVie contact person identified in Section 11.1.5 within 24 hours of the physician becoming aware of the pregnancy.

**11.2 Product Complaint**

**11.2.1 Definition**

A Product Complaint is any Complaint (see Section 11.0 for the definition) related to the biologic or drug component of the product or to the medical device component(s).

For a product this may include, but is not limited to, damaged/broken product or packaging, product appearance whose color/markings do not match the labeling, labeling discrepancies/inadequacies in the labeling/instructions (example: printing illegible), missing components/product, device not working properly, or packaging issues.

For medical devices, a product complaint also includes all deaths of a patient using the device, any illness, injury, or adverse event in the proximity of the device, an adverse event that could be a result of using the device, any event needing medical or surgical intervention including hospitalization while using the device and use errors.

Any information available to help in the determination of causality by the device to the events outlined directly above should be captured.

### **11.2.2 Reporting**

Product Complaints concerning the investigational product and/or device must be reported to the Sponsor within 24 hours of the study site's knowledge of the event via local Product Complaint reporting practices. Product Complaints occurring during the study will be followed-up to a satisfactory conclusion. All follow-up information is to be reported to the Sponsor (or an authorized representative) and documented in source as required by the Sponsor. Product Complaints associated with adverse events will be reported in the study summary. All other complaints will be monitored on an ongoing basis.

Product complaints involving a non-Sponsor investigational product and/or device should be reported to the identified contact or manufacturer, as necessary per local regulations.

Product Complaints may require return of the product with the alleged complaint condition (syringe, pen, etc.). In instances where a return is requested, every effort should be made by the investigator to return the product within 30 days. If returns cannot be accommodated within 30 days, the site will need to provide justification and an estimated date of return.

The description of the complaint is important for AbbVie in order to enable AbbVie to investigate and determine if any corrective actions are required.

## **12.0 Plans for Disseminating and Communicating Study Results**

At the end of the study, a study report will be written by AbbVie in collaboration with the principal investigator. This report will contain a description of the objectives of the

study, the methodology of the study and its results and conclusions. The completed case report forms and the study report must be treated as the confidential property of AbbVie and may not be released to unauthorized people in any form (publications or presentations) without express written approval from AbbVie. The results of this study may be published by AbbVie or by any one of the participating investigators after agreement with AbbVie.

STATISTICAL ANALYSIS PLAN

EUREKA Study

A Prospective Multi-Center study to observe the Effectiveness on Ulcerative Colitis and predictive factors of clinical response in Korean Patients treated with Adalimumab

Product Name : Adalimumab

Protocol No. : P15-346

Version : V2.0

Effective Date : 02-NOV-2018

| | | Last Update Date |
|-------------------------------|---|------------------|
| dreamcis ATIGERMED COMPANY | CONFIDENTIAL: THIS DOCUMENT AND THE INFORMATION CONTAINED HEREIN ARE PROPRIETARY TO THE COMPANY AND ARE NOT TO BE DISCLOSED WITHOUT THE WRITTEN PERMISSION OF THE COMPANY. | 02-NOV-2018 |
| | | |

STATISTICAL ANALYSIS PLAN (V2.0)

Revisions

| DATE OF REVISION | INDICATION REVISION | REASON FOR CHANGE | AUTHOR'S NAME |
|---------------------|--|---|------------------|
| | ALL | Addition of 1 st and 3 rd quartiles to the descriptive statistics | |
| | 2.5.2 PP Set | Detailed modification of the PP set selection criteria | |
| | 4.1.2 Secondary Effectiveness Evaluation | Addition of secondary effectiveness endpoints | |
| | 6. Statistical Analysis Method | Addition of the contents of the normality test | |
| | 6.2 Demographic Characteristics | Addition of p-value reporting criteria Integration of the interim analysis items | |
| | | Modification of the clinical remission criteria | |
| | 6.3.2 Secondary Effectiveness Endpoints | Precise description of analysis criterion Changes in analysis details | |
| | | Addition of secondary effectiveness endpoints | |
| 02-NOV-2018 | | Addition of nonparametric analysis method | |
| | 6.4.1 Adverse Events | Changes in the manner of description and precise description of analysis items (classified into AEs causing discontinuation of the drug and SAEs that occurred during the entire study period) Addition of "probably not" to the adverse | |
| | | drug reaction (ADR) evaluation criteria Addition of incidence rate analysis (incidence rate per 100 PTYs) | |
| | 6.4.2 Missing Data Handling and Analysis Method | Movement to item 6.7 (Missing Data Handling and Analysis Method) and addition of LOCF and mean imputation as a missing data handling method | |
| | 6.5 Exploratory Analysis | Detailed modification of the analysis method | |
| | | Addition of analysis items | |

CONFIDENTIAL:

THIS DOCUMENT AND THE INFORMATION CONTAINED HEREIN ARE PROPRIETARY TO THE COMPANY AND ARE NOT TO BE DISCLOSED WITHOUT THE WRITTEN PERMISSION OF THE COMPANY.

[figure not shown]
02-NOV-2018

Last Update Date

1.1 Introduction

Ulcerative colitis (UC) is a chronic inflammatory bowel disorder characterized by a relapsing and remitting course. In Korea, the incidence and prevalence of CD and UC are low compared to that in Europe and the USA, but are increasing rapidly. According to a recent epidemiological survey of IBD in Korea that extrapolated the national incidence from the actual measured incidence in a sample from an urban district in Seoul, the mean annual incidence of UC in Korea increased from 0.34 per 100,000 inhabitants in 1986-1990 to 3.08 per 100,000 inhabitants in 2001-2005(1). The adjusted prevalence rate of UC per 100,000 inhabitants was 30.87 (95% CI, 27.47-34.27). Genotypic features and clinical characteristics of Korean IBD are somewhat different from those seen in Western countries. For example the HLA-DRB1*1502 allele was shown to be positively associated with UC in Korea, whereas in Western populations this association is absent(2). The clinical features of UC at diagnosis are reported to be similar in Koreans and Westerners(3), however, the clinical course of UC in Korean patients seems milder than that in Western countries, as indicated by the lower rates of colectomy and better responses to pharmacological management(4). In terms of drug toxicity, Korean patients with IBD who are treated with AZA/6-MP experience myelotoxicity more frequently than similarly treated Europeans. Among 133 IBD patients treated with azathioprine in Korea, leucopenia occurred in 75 cases (56.4%), which more frequent than the rates reported in Western studies(5). In a retrospective study of infliximab in 134 Korean UC patients, the rates of clinical response and remission were 87% and 45% at week 8(6). Long-term clinical response and remission rates were 71% and 52%, respectively, and mucosal healing was the only factor influencing long-term response. Recently (2013), adalimumab was already used in the treatment of CD, was approved treating moderately to severely active UC in adults with an inadequate response to conventional therapy or who are intolerant to or have medical contraindications for such therapies. To our best knowledge, there is no published data about the effectiveness and safety of adalimumab for the treatment of UC in Korean patients. In addition, gut bacteria play an important role in the onset and perpetuation of intestinal inflammation in IBD. Some dysbiosis have been found in UC as well as Crohn's disease, and also their relationship to the clinical course of IBD has been suggested. Composition of Fecal microbiota (16S rRNA gene sequencing) will be regarded as predictive factors of clinical response in this study(7-9).

1.2 Rationale

This will be the first prospective study to evaluate the effectiveness of adalimumab in Korean patients with UC in the real-life clinical setting and to explore clinical predictive factors of response.

2. Research Methods

| | | Last Update Date |
|-------------------------------|---|------------------|
| dreamcis ATIGERMED COMPANY | CONFIDENTIAL: THIS DOCUMENT AND THE INFORMATION CONTAINED HEREIN ARE PROPRIETARY TO THE COMPANY AND ARE NOT TO BE DISCLOSED WITHOUT THE WRITTEN PERMISSION OF THE COMPANY. | 02-NOV-2018 |
| STATISTICA | LANALVSIS PLAN (V2 0) | |

STATISTICAL ANALTSIS FLAN (V2.U)

2.1 Study Design

This is a prospective, single-country, multi-center study in UC patients treated with adalimumab. The prescription of adalimumab is at the discretion of the physician in accordance with clinical practice and label, is made independently from this study and precedes the decision to offer the patient the opportunity to participate in this study.

Up to 147 subjects will be enrolled at approximately 20 sites. The baseline assessment should be performed prior to the first dose of adalimumab (Visit1). Patients will be given adalimumab 160 mg at week 0, 80 mg at week 2, and then 40 mg every other week on label. Study visits will be conducted at weeks 8, 16, 24, 32, 40, 48 and 56 after baseline in accordance with clinical practice (window period for each follow up visit will be ± 1 week). All subjects will have one Follow-up for safety approximately 70 days after the last dose of adalimumab.

Clinical response will be assessed at week 8, and patients with clinical response at week 8 will be allowed to continue on adalimumab treatment as per Korean reimbursement guidelines and will be followed up in the study.

2.2 Study Objectives

To evaluate the real world effectiveness of adalimumab in Korean UC patients through a prospective study and explore potential predictive factors of clinical response to adalimumab treatment.

2.3 Setting

2.3.1 Study Population

Subject will be adults with UC who meet the eligibility criteria.

2.3.2 Inclusion Criteria

- (1) Subject must be an adult \geq 19 years
- (2) Subject with active moderate-to-severe ulcerative colitis patients with Mayo score of ≥ 6 points and endoscopic sub-score of ≥ 2 points despite treatment with corticosteroids and/or immunosuppressants.
- (3) Subject who must have tuberculosis (TB) Screening Assessment in accordance with Korean reimbursement guideline
- (4) Subjects who are started on adalimumab treatment in normal clinical practice setting by their physician.
- (5) Subject must provide written authorization form to use personal and/or health data prior to the entry into the study

2.3.3 Exclusion Criteria

| | | Last Update Date |
|-------------------------------|--|------------------|
| dreamcis ATIGERMED COMPANY | CONFIDENTIAL: THIS DOCUMENT AND THE INFORMATION CONTAINED HEREIN ARE PROPRIETARY TO THE COMPANY AND ARE NOT TO BE DISCLOSED | 02-NOV-2018 |
| STATISTICA | WITHOUT THE WRITTEN PERMISSION OF THE COMPANY. LANALYSIS PLAN (V2.0) | |

- (1) Female subjects who are pregnant or breast feeding
- (2) Subjects with any contraindication to adalimumab
- (3) Subjects that is participating in other clinical trials

2.4 Study Size

The primary endpoint of this study is to investigate the effectiveness of adalimumab in Korean patients with Ulcerative Colitis (UC) in real life settings. With reference to adalimumab real life data in UC, clinical response rate to adalimumab at week 12 was about 75% (10). Assuming 95% confidence interval, 15% confidence interval width and an estimated drop-out rate of 5%, we aim to recruit up to 147 subjects in this study.

2.5 Data Analysis Set

The study population will be classified by ITT (Intend-To-Treat) set and PP (Per-Protocol) set.

2.5.1 ITT Set

The ITT set will include all subjects intended to treat with adalimumab.

At week 8, all subjects who have received adalimumab treatment at least once will be included and, at week 56, all subjects who have clinical response at week 8 will be included.

2.5.2 PP Set

The PP set will include all subjects who meet the eligibility criteria for this study and complete the evaluation without any major protocol deviation among the ITT set.

At week 8, all subjects who meet the eligibility criteria and complete the evaluation at week 8 will be included and at week 56, all subjects who complete the evaluation and the study follow-up without any major protocol deviation.

2.5.3 Principles of Analysis

Demographics and safety will be analyzed by ITT set and effectiveness will be analyzed in the ITT and PP set.

3. Drop-out Subjects

Subjects who meet the below categories will be dropped out from the study.

- (1) If the subjects choose to withdraw from the study
- (2) Where ethical or practical conflicts hinder the procedure of the study, and such cases will be determined

| | | Last Update Date |
|----------------------------------|---|------------------|
| dreamcis ATIGERMED COMPANY | CONFIDENTIAL: THIS DOCUMENT AND THE INFORMATION CONTAINED HEREIN ARE PROPRIETARY TO THE COMPANY AND ARE NOT TO BE DISCLOSED WITHOUT THE WRITTEN PERMISSION OF THE COMPANY. | 02-NOV-2018 |
| STATISTICAL ANALYSIS PLAN (V2.0) | | |

based on the investigator's judgment

(3) In case of Adalimumab discontinuation at any point during study period

4. Variables

4.1 Effectiveness

If necessary, the analysis for week 24 will be performed for interim results.

4.1.1 Primary Endpoint

Clinical response at week 8, 24, and 56

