#### **Primary Endpoint:**

- The percentage of patients with clinical response at week 8

- The percentage of patients with clinical response at week 56 in week 8 responders

Clinical response is defined as reduction in complete Mayo score of  $\geq 3$  points and  $\geq 30\%$  from Baseline (Week 0) with an accompanying decrease in rectal bleeding subscore of  $\geq 1$  point or absolute rectal bleeding subscore of  $\leq 1$  point at week 8.

Durable clinical response is defined as reduction in complete Mayo score of  $\geq 3$  points and  $\geq 30\%$  from Baseline (Week 0) with an accompanying decrease in rectal bleeding subscore of  $\geq 1$  point or absolute rectal bleeding subscore of  $\leq 1$  point at both week 8 and 56.

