6.3 Effectiveness Endpoint Analysis Method

6.3.1 Primary Effectiveness Endpoint

- (1) The frequency and percentage of the subjects who showed a clinical response^a at visit 2 (week 8) will be presented, and the 95% confidence interval will be calculated.
- (2) The frequency and percentage of the subjects who showed a persistent clinical response^a at visit 2 (week 8), visit 4 (week 24), and visit 8 (week 56) will be presented, and the 95% confidence interval will be calculated.

Here, if any item in either the full or partial Mayo score was not collected, the subject will be excluded from this analysis.

^a Clinical response: It is defined as the case with 3 points or more reduction and 30% or more reduction in the full Mayo score at visit 2 (week 8) from visit 1 (baseline) plus 1 point or more reduction in the rectal bleeding subscore or an absolute rectal bleeding subscore of 1 point or less.

^b Persistent clinical response: Defined as the case of 3 points or more reduction and 30% or more reduction in the full Mayo score both at visit 2 (week 8) and visit 8 (week 56) from visit 1 (baseline) plus 1 point or more reduction in the rectal bleeding subscore or absolute rectal bleeding subscore of 1 point or less. At visit 4 (week 24), however, it is defined as the case of 2 points or more reduction and 30% or more reduction in the partial Mayo score plus 1 point or more reduction in the rectal bleeding subscore or an absolute rectal bleeding subscore of 1 point or less.

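### SAP 4.1.1 and 6.3.1(2) do not state the protocol's second primary endpoint: they add week 24 on another criterion, leave the visit rule open and name no denominator

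*SAP*

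**What the plan says.** **Protocol.** The abstract, section 9.1 and section 9.7 give the same two primary endpoints: response at week 8, and "The percentage of patients with clinical response at week 56 in week 8 responders". Section 9.1 defines durable response by the complete Mayo criteria at week 8 and at week 56. Week 24 is not a primary time point anywhere. Section 9.3 schedules only a partial Mayo score at that visit.

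**SAP endpoint text.** Section 4.1.1 gives the primary endpoint as "Clinical response at week 8, 24, and 56". Section 6.3.1(2) counts, with a 95% CI, the subjects who "showed a persistent clinical response^a at visit 2 (week 8), visit 4 (week 24), and visit 8 (week 56) will be presented". The marker there points to footnote a, which defines response at week 8. Persistent response is defined in footnote b: full Mayo criteria at weeks 8 and 56, with a separate week-24 rule (partial Mayo down by at least 2 points and 30%, plus the same rectal-bleeding condition). Section 4.1 says of week 24: "If necessary, the analysis for week 24 will be performed for interim results".

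**SAP analysis sets.** Section 2.5.1 states that "at week 56, all subjects who have clinical response at week 8 will be included". The PP set (2.5.2) takes those who "complete the evaluation without any major protocol deviation among the ITT set", and 2.5.3 says "effectiveness will be analyzed in the ITT and PP set". Neither 4.1.1 nor 6.3.1(2) repeats the responder restriction. Items (1) to (4) of 6.3.2 do state it for the later visits.

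**SAP missing data.** Section 6.3.1 leaves out of the primary analysis any subject with an uncollected full or partial Mayo item. Section 6.6 carries the last value forward for partial Mayo items and does not replace a missing endoscopic subscore.

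**The concern.** This is a single-arm, descriptive study, so the reported percentage and its interval are the result. The protocol fixes one definition for the week-56 primary. The SAP text leaves four things to whoever programs it:

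- whether week 24 is part of the primary endpoint or an interim look;
- whether the three visits are three separate rates or one joint condition;
- which footnote defines the event;
- which subjects form the denominator, above all at week 24.

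SAP V2.0 is dated 02-NOV-2018. The protocol planned to end data collection in 2Q 2017. Actual dates are not given, but these choices may be made with the data in hand.

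**Working it through.** **1. The two definitions side by side**

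| Element | Protocol 9.1 / 9.7 | SAP 4.1.1 / 6.3.1(2) |
|---|---|---|
| Visits | 56 (durable: 8 and 56) | 8, 24 and 56 |
| Scale | Full Mayo | Full Mayo at 8 and 56; partial Mayo at 24 |
| Point threshold | 3 points and 30% | 3 points and 30%; at week 24, 2 points and 30% |
| Denominator | Week-8 responders | Not stated (2.5.1 supplies it for week 56, nothing for week 24) |

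**2. One line cannot carry one responder denominator.** Over week-8 responders, the week-8 entry in 6.3.1(2) is 100% by construction. Either the denominator changes within the line, or the line uses all treated subjects. The text does not say which.

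**3. Joint reading.** Let r56 be the week-56 response rate among week-8 responders, and q the share of those week-56 responders who also met the week-24 rule. The joint rate is r56 × q, a fall of r56 × (1 − q), which is zero or more. The documents give no q, so the size cannot be computed. For scale only, at r56 = 0.71 each 10% of durable responders who miss the week-24 rule costs 0.71 × 0.10 = 7.1 points.

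**4. Exclusion for an uncollected week-24 item.** Let x of N responders respond at week 56. Suppose m subjects are removed under 6.3.1, of whom y responded at week 56. The rate goes from x/N to (x − y)/(N − m). It is unchanged only if y/m = x/N, and it rises if those removed did worse. The documents give neither m nor y. Under 6.6 the same partial Mayo item would be carried forward, so the two sections give different answers for the same subject.

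**5. All-treated denominator**

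The plan's own figure comes first. An exact (Clopper-Pearson) 95% interval of total width 0.15 at a rate of 0.75 needs n = 139 (width 0.14999, with a fractional expected count of 0.75 × 139 = 104.25). Then 139/0.95 = 146.3, rounded up to 147, which matches the stated size.

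Inputs:
- r8 = 0.75, the planning rate in protocol 9.5 (a week-12 adalimumab rate);
- r56 = 0.71, the only long-term response rate in the documents (protocol 7.1: a retrospective infliximab study, denominator not stated);
- r8 = 0.87 as an alternative, the week-8 rate from that same infliximab study;
- r56 = 0.50 and 0.90 as assumed bounds.

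The rate over responders is r56. Over all treated it is r8 × r56, if everyone without a week-8 response counts as a failure. The gap is r56 × (1 − r8).

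| r8 | r56 = 0.50 | r56 = 0.71 | r56 = 0.90 |
|---|---|---|---|
| 0.75 | 12.5 points | 17.75 points | 22.5 points |
| 0.87 | 6.5 points | 9.2 points | 11.7 points |

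In counts: 0.75 × 147 = 110 responders and 0.71 × 110 = 78 with week-56 response, so 78/110 = 71% against 78/147 = 53%. For scale, the exact 95% interval for 78/110 is 17.7 points wide in total. If 2.5.1 is applied at week 56, the denominator is the 110 and the gap is zero.

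**The case against.** A reader might infer that the SAP drops the restriction to week-8 responders, and that the headline rate therefore moves by 18 points. The documents do not support that. SAP 2.5.1 limits the week-56 ITT set to week-8 responders, as protocol 9.7 does. The PP set is drawn from the ITT set, and 2.5.3 applies both to effectiveness. The all-treated rate is also hard to reach from the SAP's own rules. Subjects who stop adalimumab are dropped from the study (SAP section 3), and under 6.3.1 a subject without the week-56 Mayo items leaves the analysis and is not counted as a failure. This part of the defence stands.

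A reader might also infer that the week-24 visit is optional. It is a scheduled visit with a partial Mayo score. Only the interim analysis is conditional.

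The joint three-visit reading is not the most natural one. Footnote b ties persistence to weeks 8 and 56 and then sets out week 24 separately. SAP 6.5(1) speaks of persistent response at weeks 8 and 56 only, and the title of 6.5(4) refers to each visit. This makes separate reporting more likely but does not settle it, because 6.3.1(2) lists the three visits with no such statement.

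The footnote marker may be a typing slip or an artefact of reading the PDF. Footnote b carries the title of the term, so the intended definition can be recovered. Finally, the study is descriptive and has no primary hypothesis test, so no type I error is at risk.

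The defence does not remove three facts: week 24 sits in the SAP's primary endpoint and not in the protocol's, no analysis set is defined for it, and the primary text omits a denominator that the secondary text states.

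**Conclusion.** The concern holds as a conflict between SAP and protocol on a primary endpoint. SAP 4.1.1 and 6.3.1(2) add a week-24 component on a different scale and threshold, which SAP 4.1 itself treats as interim. They leave the visit rule open, point to the wrong footnote and do not state the denominator.

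The size is not a single number. A joint reading can only lower the week-56 rate or leave it unchanged, and exclusion for an uncollected week-24 item can move it either way. The documents allow neither to be computed. The denominator effect is zero if 2.5.1 is followed. It becomes about 18 points, with a range of 6.5 to 22.5, only if an analyst departs from 2.5.1. Those figures rest on assumed inputs, and the central one pairs a week-12 adalimumab rate with a long-term infliximab rate whose denominator is unknown. They show what an explicit denominator protects against, not what the SAP prescribes.

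**What to change.** In SAP 4.1.1 and 6.3.1(2):

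- Define the second primary as the number of subjects with full-Mayo response at week 56 (footnote b, limited to weeks 8 and 56) divided by the number of week-8 responders, which is the week-56 ITT set of 2.5.1, with its 95% CI.
- Correct the marker on persistent response from a to b.
- Move week-24 partial-Mayo response to a secondary or supportive endpoint, with its own stated denominator and as a separate rate.
- State that a missing week-24 item does not remove a subject from the week-56 primary analysis, and align 6.3.1 with 6.6 on this.

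The change is to SAP wording only, with no new data. Its cost is that week 24 loses its primary label.
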